## 4 STUDY DESIGN

### 4.1 Overall design

ONC001 is a multicenter, nonrandomized, open-label, Phase 1/2 study evaluating the safety, PK, and antitumor activity of iv UCB6114 in participants with advanced solid tumors.

The study has a modular design including up to 3 dose escalation modules (Parts A, B, and C), 1 dose optimization module (Part A1), and up to 4 expansion modules (Parts D, E, F, and G) (see Section 1.2). Depending on emerging data, not all modules may open.

After completion of Part A, Part A1, Part B, and Part C, specific characteristics of modules subsequent to Part A, Part A1, Part B, and Part C will be described in planned protocol amendments. The updated characteristics will include, but not be limited to, tumor type selection, participant's inclusion/exclusion criteria, route and frequency of study medication administration, and selection of the SOC treatment regimen.

There are 8 different study modules for dose escalation and expansion, which are shown in [Table 4-1](#).

**Table 4-1: Study modules for dose escalation and expansion**

Module	Module description
Part A	Dose-escalation to identify the RP2D-M, based on emerging safety, PK, PD, and antitumor effect data. Participants will receive UCB6114 Q2W via iv infusion. The starting dose will be escalated (or de-escalated) stepwise in successive cohorts of 3 to 6 evaluable participants (modified rolling-6 design) (see Section 4.1.2), until the RP2D-M is determined. Up to 42 participants may be enrolled.
Part A1	Dose-optimization to evaluate alternative dosing schedules for UCB6114 administered as monotherapy in participant with unresectable locally advanced or metastatic colorectal adenocarcinoma, gastric adenocarcinoma, adenocarcinoma of the gastroesophageal junction, or pancreatic cancer. Based on emerging data from Part A, this module will evaluate a new dose formulation, different frequencies of dosing (eg, Q3W, QW4), and different time of infusion. Up to 32 participants may be enrolled.
Part B	Dose-escalation with TFD/TPI in participants with unresectable locally advanced or metastatic colorectal adenocarcinoma, gastric adenocarcinoma, or adenocarcinoma of the gastroesophageal junction to identify the RP2D-T.  The starting dose of UCB6114 in Part B will depend on the dose level evaluated in Cohort 3 of Part A (anticipated to be 500mg Q2W iv) and the emerging safety profile of UCB6114 monotherapy, including any overlapping toxicity with TFD/TPI. It is expected that 2 or 3 dose levels of UCB6114 will be explored. The starting dose will be escalated stepwise in successive cohorts of 2 to 4 evaluable participants (mTPI design), until the RP2D-T is determined. Up to 27 participants may be enrolled.
Part C	Dose-escalation with mFOLFOX6 in participants with unresectable locally advanced or metastatic colorectal adenocarcinoma, gastric adenocarcinoma, and adenocarcinoma of the gastroesophageal junction to identify the RP2D-F.  The starting dose of UCB6114 in Part C will depend on the dose level evaluated in Cohort 3 of Part A (anticipated to be 500mg Q2W iv), and the emerging safety profile of UCB6114 monotherapy, including any overlapping toxicity with the mFOLFOX6 regimen. The starting dose and dose escalation scheme may differ from that evaluated in Part B. It is expected that 2 or 3 dose levels of UCB6114 will be explored. The starting dose will be escalated stepwise in successive cohorts of 2 to 4 evaluable participants (mTPI design), until the RP2D-F is determined. Up to 27 participants may be enrolled.
Part D	Expansion module to explore the safety and antitumor activity of UCB6114 as monotherapy with the RP2D-M dosing regimen. It is planned to evaluate 15 participants with a selected recurrent/metastatic tumor type 1 (to be decided based on emerging internal and external data). Up to 15 additional participants may be enrolled depending on the observed antitumor activity (total sample size of up to 30 participants).

**Table 4-1: Study modules for dose escalation and expansion**

Module	Module description
Part E	Expansion module to explore the safety and antitumor activity of UCB6114 as monotherapy with the RP2D-M dosing regimen in an alternative selected tumor type (tumor type 2). It is planned to evaluate 15 participants with a selected recurrent/metastatic tumor type 2 (to be decided based on emerging internal and external data). Up to 15 additional participants may be enrolled depending on the observed antitumor activity (total sample size of up to 30 participants).
Part F	Expansion module to explore the safety and antitumor activity of UCB6114 in combination with the SOC regimen tested in Part B (RP2D-T). It is planned to evaluate UCB6114 plus SOC in 15 participants with a selected recurrent/metastatic tumor type. Up to 15 additional participants may be enrolled depending on the observed antitumor activity (total sample size of up to 30 participants).
Part G	Expansion module to explore the safety and antitumor activity of UCB6114 in combination with the SOC regimen tested in Part C (RP2D-F). It is planned to evaluate 15 participants with a selected recurrent/metastatic tumor type. Up to 15 additional participants may be enrolled depending on the observed antitumor activity (total sample size of up to 30 participants).

iv=intravenous(ly); mFOLFOX6=leucovorin 400mg/m^2 on Day 1, 5-fluorouracil 400mg/m^2 on Day 1 + 1200mg/m^2/day on Day 1 and Day 2, and oxaliplatin 85mg/m^2 on Day 1; mTPI= modified toxicity probability interval; QW=once weekly; Q2W=every 2 weeks; Q3W=every 3 weeks; PD=pharmacodynamics; PK=pharmacokinetics; RP2D-F=recommended Phase 2 dose of UCB6114 when used in combination with FOLFOX; RP2D-M=recommended Phase 2 dose for monotherapy; RP2D-T=recommended Phase 2 dose of UCB6114 when used in combination with TFD/TPI; sc=subcutaneous; SOC=standard of care; TFD/TPI=trifluridine/tipiracil

In Part A, each cohort will include 3 to 6 participants. Dose escalation (or de-escalation) will be guided by safety assessments and available PK data. At each dose level, PD samples will be collected to evaluate the PK/PD relationship.

In Part A, eligible participants will receive UCB6114 as an iv infusion every 2 weeks (Q2W) as monotherapy. UCB6114 will be administered as a flat dose (ie, not adjusted for weight or body surface area [BSA]) unless emerging data indicate that weight- or BSA-based dosing would be more appropriate. Doses of UCB6114, ranging from 100mg to 2000mg (corresponding to approximately 1 to 30mg/kg) (Table 6-5) may be explored. Five dose levels are planned; however, an additional 2 dose levels may be added based on emerging data. Dose escalation steps are currently planned at a maximum of 2.5-fold; however, may be adjusted based on observed PK in the preceding cohort(s) and will not exceed 5-fold. Up to 42 participants may be enrolled.

The planned duration of treatment is 2 cycles. Participants may, however, remain on study for additional cycles if they are receiving therapeutic benefit (stable disease [SD], partial response [PR], or complete response [CR]) or until they fulfill one of the criteria for study discontinuation. Upon discontinuation of treatment, participants will be referred to appropriate follow-up care per the investigator's judgment.

Part A will include participants with tumor types associated with expression of *GREM1* mRNA. These tumor types include bladder urothelial carcinoma, breast invasive carcinoma, colorectal

adenocarcinoma, esophageal carcinoma, head and neck squamous cell carcinoma, lung adenocarcinoma, lung squamous cell carcinoma, pancreatic adenocarcinoma, prostate adenocarcinoma, and stomach adenocarcinoma based on *GREM1* expression data from Sneddon et al, 2006 and the Cancer Genome Atlas (The Cancer Genome Atlas, 2019).

From Part A, a RP2D for UCB6114 monotherapy (RP2D-M) will be selected based upon the totality of information, including the safety profile, PK profile, and available antitumor activity and PD data. The start of any modules subsequent to Part A (monotherapy dose escalation) will be reliant on module-specific criteria and the approval of planned protocol amendments.

Part A1 will be initiated after Cohort 5 of Part A (2000mg Q2W) has been determined to be [REDACTED] (ie, DLT incidence <33%, see Section 4.1.2.4). Eligible participants with unresectable locally advanced or metastatic colorectal adenocarcinoma, gastric adenocarcinoma, adenocarcinoma of the gastroesophageal junction, or pancreatic cancer will receive iv infusion of UCB6114 as monotherapy. Four alternative dosing schedules (cohorts) have been planned and will explore shorter infusion time, and less frequent administration (Table 6-6). Each cohort will enroll 8 participants including 1 sentinel participant. Up to 32 participants may be enrolled.

Part B and Part C of ONC001 are planned to be initiated after Cohort 3 of Part A has completed the 28-day DLT assessment period and once the SMC has provided a recommendation to dose escalate to the next protocol-defined level in Part A of the study. For all dose levels, participants will be treated in cohorts of 2 to 4 (target of 3), each dose level will have a minimum of 3 and a maximum of 9 participants (Section 4.1.4.2.2 [Part B] and Section 4.1.5.2.2 [Part C]).

In Part B, eligible participants with unresectable locally advanced or metastatic colorectal adenocarcinoma, gastric adenocarcinoma, or adenocarcinoma of the gastroesophageal junction will receive UCB6114 as an iv infusion in combination with orally administered TFD/TPI. The initial dose and schedule of UCB6114 will depend on the dose level evaluated in Cohort 3 of Part A (anticipated to be 500mg Q2W iv), the emerging safety profile of UCB6114 monotherapy, and any predicted overlapping toxicities with TFD/TPI. Up to 3 dose levels (anticipated to be 500mg, 1000mg, and 2000mg administered Q2W iv) are planned (Section 4.3.3). Up to 27 participants are planned. Dose escalation decisions in this module will be guided by a model-based estimation of the probability of DLT in Cycle 1.

In Part C, eligible participants with unresectable locally advanced or metastatic colorectal adenocarcinoma, gastric adenocarcinoma, or adenocarcinoma of the gastroesophageal junction will receive UCB6114 as an iv infusion in combination with mFOLFOX6 chemotherapy. The initial dose and schedule of UCB6114 will depend on the dose level evaluated in Cohort 3 of Part A (anticipated to be 500mg Q2W iv), the emerging safety profile of UCB6114 monotherapy, and any predicted overlapping toxicities with mFOLFOX6. Up to 3 dose levels (anticipated to be 500mg, 1000mg, and 2000mg administered Q2W iv) are planned (Section 4.3.3). Up to 27 participants are planned. Dose escalation decisions in this module will be guided by a model-based estimation of the probability of DLT in cycle 1.

In the expansion modules, the RP2D from the respective escalation modules (Part A through Part C) will be tested either as monotherapy in selected tumor types (Part D and Part E) or in combination with SOC (Part F and Part G). Participants recruited to these modules must have at least 1 measurable tumor lesion according to relevant Response Evaluation Criteria in Solid Tumors (RECIST).

Participants will continue treatment until disease progression, unmanageable toxicity, criteria for discontinuation are met, or withdrawal of consent.

In the dose escalation modules, the decision to proceed to the next dose cohort will occur once all participants in the preceding cohort have been monitored for a minimum of 28 days (ie, 1 cycle). However, all available safety data (both within the cohort and from preceding cohorts) will be taken into consideration when dose escalation decisions are made.

In the expansion modules, response will be assessed after completion of 2 cycles of treatment (ie, 4 doses on Q2W dosing regimen) and at regular intervals thereafter.

#### **4.1.1 Study oversight**

Study safety oversight will be performed via an SMC as well as regular safety conference calls in Part A, and by an SMC and an SSC, as well as regular safety conference calls, once modules subsequent to Part A commence.

#### **Safety monitoring committee**

A SMC will be established for Part A and will comprise key Sponsor personnel and Investigators from participating sites. Once modules subsequent to Part A commence, the members of the SMC will include Investigators who are actively enrolling study participants into the study.

Responsibilities of the SMC include:

- Review of safety data for study participants including review and provision of adjudication of individual DLTs, when applicable.
- Review of available PK and PD biomarker data.
- Make dose escalation recommendations, dosing schedule recommendations, recommendations to continue the study as planned or with protocol adjustments, if needed.
- Determination of the MTD, if applicable.

#### **Study steering committee**

An SSC will be implemented prior to the start of modules subsequent to Part A. The SSC members will include the coordinating Investigator, supporting co-Investigators, and clinical experts not involved in the study. The medical, scientific, and clinical study expertise of the SSC will assist the Sponsor in identifying and resolving study related issues, such as study design, study implementation and conduct, and data analysis and reporting. In consultation with the SMC, the SSC will recommend to the Sponsor the dose and dosing regimen to be taken forward for Part B and Part C.

#### **4.1.2 Part A – Monotherapy dose escalation**

In Part A of the study, 3 to 6 participants will be enrolled per dose level using a modified rolling-6 design. The rolling-6 design is an algorithm-based design in which a total of 6 participants can be enrolled at the same dose level. The modification requires that each dose level incorporates a sentinel participant. The enrollment of a sentinel participant in each cohort has been included as an additional risk mitigation measure to monitor infusion related reactions and other early onset treatment related AEs. Each sentinel participant will be assessed for at least 24 hours following second treatment administration before further participants within the dose

cohort can be enrolled. In the absence of a DLT observation in the sentinel participant after 16 days, the remaining 5 participants may be enrolled concurrently ([Figure 4-1](#)). Should the sentinel participant experience a DLT, then participants 2 and 3 will be enrolled and observed for 16 days ([Figure 4-2](#)). Escalation can be performed when 3/3, 4/4, 5/5, 5/6, or 6/6 participants are evaluated without a DLT. When a single DLT has been observed in a given dose level, participants will be included at the same dose level, up to a total of 6 participants. De-escalation occurs when 2 or more participants experience a DLT at the first dose level.

Dose escalation requires at least 3 participants to be treated and observed for at least 28 days after the first dose (assuming UCB6114 is dosed Q2W). If dosing is less frequent (due to missed or delayed doses or due to a planned change in schedule), at least 3 participants should be treated and observed for a minimum of 28 days (ie, 1 cycle), before dose escalation is considered. The second participant in any new cohort should also not be dosed until the first participant has received at least 2 doses and been observed for a minimum of 16 days (ie, 24 hours following the second treatment administration). All participants will remain in the hospital or study site's standard monitoring facility for continuous monitoring for the first 24 hours following the first dose; at subsequent doses, the participant may remain at the hospital or study site's standard monitoring facility at the investigator's discretion.

#### **4.1.2.1 SMC**

[figure not shown]
Once the last participant in a given cohort has completed the required 28-day DLT Observation Period, an SMC meeting will be convened to review all safety data, available PK data, and any available PD data. The SMC will decide whether to halt dose escalation, further expand the cohort to gain additional safety data, or determine the next dose level to be tested. Details are described in an SMC Charter.

#### **4.1.2.2 Dose escalation criteria**

Dose-limiting toxicities observed in the full 28 days of Cycle 1 will be used to decide whether escalation to the next dose level may take place or whether cohort expansion or dose de-escalation should occur. However, all available safety data (both within the cohort and from preceding cohorts) will be taken into consideration when making such decisions.

Dose-limiting toxicities may not be encountered in this study. There is no intention to continue dose escalation until an MTD can be established. The decision-making guidelines for dose escalation are shown in [Figure 4-1](#) (no DLT was observed in the sentinel participant) and [Figure 4-2](#) (a DLT was observed in the sentinel participant). The SMC will make dose escalation decisions based upon review of safety data and available PK data after all participants in a cohort complete at least the first treatment cycle (28 days) or have discontinued.

[figure not shown]
**Figure 4-1: Dose escalation decision making: no DLT observed in sentinel participant**

DLT=dose-limiting toxicity; MTD=maximum tolerated dose

Note: Figure 2 is shown in [Figure 4-2](#).

**Figure 4-2: Dose escalation decision making: DLT observed in sentinel participant**

DLT=dose-limiting toxicity; MTD=maximum tolerated dose

#### 4.1.2.3 Dose de-escalation following initial dose level

The SMC will determine if a dose de-escalation may be warranted, for example, if DLTs are observed in ≥2 participants in Cohort 1.

#### 4.1.2.4 Dose-limiting toxicity determination and maximum tolerated dose definition

Dose-limiting toxicity is defined as an AE that is at least possibly related to the study medication that occurs during Cycle 1 and fulfills any one of the following criteria:

1. Grade 3 or 4 nonhematological toxicity according to the National Cancer Institute (NCI) Common Terminology Criteria for AEs (CTCAE Version 5.0) except for alopecia (of any severity or duration), or nausea, vomiting, or diarrhea that reverses to Grade ≤2 within 24 hours with appropriate medical therapy.
2. Grade 3 or 4 biochemical abnormality that persists despite maximal supportive treatment or biochemical abnormalities that is symptomatic and nontransient (does not return to baseline within 24 hours, with or without appropriate supplementation).
3. Any Grade ≥3 hematological toxicity of >5 days duration or febrile neutropenia (absolute neutrophil count [ANC]<1000/mm^3 with a single temperature of >38.3°C or sustained temperature ≥38°C for more than one hour), infection (documented clinically or

microbiologically) with Grade 3 or 4 neutropenia, thrombocytopenia with bleeding or requiring platelet transfusion, or Grade 4 thrombocytopenia.

4. Prolonged Grade 2 diarrhea (>7 days) despite adequate antidiarrheal medication, or multiple Grade 1 or 2 toxicities (eg, Grade 1 or 2 diarrhea, vomiting, rash, and fatigue) may also be considered dose-limiting if considered so by the investigator.

Investigators, in consultation with the study physician or medically qualified designee, can declare a DLT if a participant is experiencing toxicity and treatment cannot be continued without exposing the participant to excessive risk.

The MTD is considered to be the dose level immediately below that which results in a DLT incidence of 33% or higher.

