**Table 3-1: Objectives and endpoints for the dose escalation module (Part A) and the dose optimization module (Part A1)**

Objectives	Endpoints
Primary	
To characterize the safety profile of UCB6114 as monotherapy	Incidence of TEAEs Severity of TEAEs Incidence of DLTs
Secondary	
To characterize the PK of UCB6114 administered as monotherapy	UCB6114 concentration by scheduled assessment and cohort
Tertiary/exploratory	
To document any antitumor activity observed with UCB6114 according to relevant RECIST criteria	Antitumor activity as indicated by: 

• ORR

• DCR

• DOR

• PFS

• OS

To explore PD biomarkers of UCB6114	

• Change in transcriptional and protein marker levels in blood and tumor tissue by scheduled assessment and cohort

• Change in ctDNA levels in blood by scheduled assessment and cohort

To evaluate the incidence, emergence, and impact of ADA	ADA (anti-UCB6114 antibody) titer and sample status by scheduled assessment

ADA=antidrug antibody; ctDNA= circulating tumor DNA; DCR=disease control rate; DOR=duration of antitumor response; DLT=dose-limiting toxicity; ORR=objective response rate; OS=overall survival; PD=pharmacodynamic(s); PFS=progression-free survival; PK=pharmacokinetic(s); RECIST=Response Evaluation Criteria in Solid Tumors; TEAE=treatment-emergent adverse event

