#### **4.1.3 Part A1 – Dose optimization (alternative dosing schedules)**

Part A1 is a multicenter, non-randomized, open-label, dose optimization module of Study ONC001 to evaluate alternative dosing schedules and infusion times for UCB6114 administered as monotherapy in patients with unresectable locally advanced or metastatic colorectal cancer, gastric cancer, cancer of the gastro-esophageal junction, or pancreatic cancer.

Part A1 may commence after the fifth cohort in Part A (Cohort 5) is considered sufficiently █ by the SMC (DLT rate less than 33%). The planned dose optimization scheme for Part A1 will assess the safety and tolerability of the drug new formulation and will explore shortening of the infusion time and less frequent dosing as follows:

- Cohort 1: 2000mg Q2W (60-minute iv infusion), 28-day treatment cycle
- Cohort 2: 2000mg Q2W (30-minute iv infusion), 28-day treatment cycle
- Cohort 3: 3000mg Q3W (90-minute iv infusion), 21-day treatment cycle
- Cohort 4: 4000mg Q4W (120-minute iv infusion), 28-day treatment cycle

Details of each planned cohort are provided in [Table 6-6](#).

Up to 32 participants will be allocated 1:1:1:1 to one of the 4 cohorts, with each cohort enrolling 8 study participants including 1 sentinel participant with an observation period of 48 hours.

The enrollment of a sentinel participant in each cohort has been included as an additional risk mitigation measure to monitor infusion related reactions and other early onset treatment-related AEs. Each sentinel participant will be assessed for at least 48 hours following the first administration of UCB6114 in the first cycle and the SMC will convene before further participants within the cohort can be enrolled.

The SMC will also convene after 25%, 50% and 100% of study participants in Part A1 have completed the required 28-day observation period. If deemed necessary, an additional SMC meeting can convene after 75% of the participants have completed the required observation period. If 1 DLT, or more, (refer to Section 4.1.2.4 for the definition of DLTs) are reported for a cohort then, an ad-hoc SMC will convene to determine if the dosing schedule and study can continue as planned.

If 3 or more participants experience DLT(s) in a given cohort, no further participants will be enrolled in the cohort and the dosing schedule will be considered to be unacceptably toxic.

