#### **4.1.4.2 Dose-limiting toxicity and maximum tolerated dose definition and determination**

##### **4.1.4.2.1 Definition of DLT**

Dose-limiting toxicity is defined as one of the following toxicities (according to the NCI CTCAE Version 5.0) occurring during the DLT assessment window (Days 1 to 28 of Cycle 1) that is at least possibly related to UCB6114:

- Grade  $\geq 4$  neutropenia (ANC  $<500/\mu\text{L}$ ) lasting  $\geq 7$  days
  - In the event of CTCAE Grade 4 neutropenia, full blood count must be performed on the seventh day after the onset of the event to determine if a DLT has occurred
- Grade  $\geq 3$  neutropenia complicated by fever ( $\geq 38^\circ \text{C}$ ) or infection
- Grade 3 thrombocytopenia with bleeding or requiring platelet transfusion or Grade 4 thrombocytopenia
- Any Grade  $\geq 3$  non-hematological event with the following exceptions:

---

- Grade 3 nausea, vomiting, diarrhea, or fatigue that resolves to Grade  $\leq 2$  within 24 hours of implementing optimal supportive care
- Grade 3 laboratory abnormality that is asymptomatic and also deemed by the investigator to not be clinically significant

Investigators, in consultation with the medical monitor, can declare a DLT if a participant is experiencing toxicity and treatment cannot be continued without exposing the participant to excessive risk.

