### 6.6.2.2 UCB6114 dose modifications

Study participants who experience Grade 4 (life-threatening) nonhematologic toxicity, including diarrhea and mucositis, which is at least possibly related to UCB6114, will be discontinued from treatment.

Treatment with UCB6114 may temporarily be suspended for up to 3 weeks beyond the scheduled treatment day until toxicities are resolved to CTCAE Grade 2 or less. If UCB6114 is

held for more than 3 weeks beyond the scheduled treatment day, then the participant will be discontinued from treatment and will be followed up for safety and efficacy per the Schedules of Activities for Part A ([Table 1-4](#)), Part B ([Table 1-7](#)), and Part C ([Table 1-8](#)).

For permitted adjustments of the infusion rate in case of AEs refer to the IMP Handling Manual. Participants who experience severe or life-threatening infusion-related events (CTCAE Grade 3 or 4) will not receive further infusions. Hypersensitivity/infusion-related events should be managed per institutional guidelines. Premedication with steroids may be administered at the discretion of the investigator.

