## 10.3 Planned safety and other analyses

### 10.3.1 Safety analyses

Safety will be assessed by clinical review of all relevant parameters including AEs, SAEs, laboratory values, vital signs, echocardiograms, ECG results and physical examination. Eastern Cooperative Oncology Group performance status will also be assessed from a safety perspective. Unless specified otherwise, the safety analyses will be conducted for the SS defined in Section 10.1. The results of these analyses will be presented by study part. For the dose escalation modules of the study (Part A, B, and C) tabulations will be provided by dose level and overall. For the dose optimization module of the study (Part A1) tabulations will be provided by cohort and overall. For the expansion modules (Parts D, E, F, and G), tabulations will be

provided by tumor type and overall. Some safety analyses may be performed based on the dose escalation, optimization, and expansion modules combined.

Summary tables and listings will be provided for all reported TEAEs, defined as AEs that start on or after the first administration of study treatment up until the SFU visit. A pre-treatment AE which increases in severity on or after the first dose of study treatment will also be counted as a TEAE. The reported AE term will be assigned a standardized preferred term using the current version of the Medical Dictionary for Regulatory Activities (MedDRA).

The causal relationship between the occurrence of an AE and study medication will be judged by the investigator. In the event that a participant experiences repeat episodes of the same AE, then the event with the highest CTCAE severity grade and strongest causal relationship to study medication will be used for purposes of incidence tabulations.

An overview of the number and percentage of participants who experience TEAEs will be presented. This summary will include the number and percentage of participants with any TEAEs, serious TEAEs, related TEAEs (related to UCB6114, TFD/TPI [Part B], any individual component of mFOLFOX6 [Part C], or more than 1 of the treatments [Part B and Part C]), discontinuation due to TEAEs, CTCAE Grade 3 or 4 TEAEs, DLTs, AEs leading to death, and TEAEs leading to death; event counts will also be included against each of these categories.

In addition, the following summaries will be presented by MedDRA System Organ Class, High Level Term and Preferred Term:

- Incidence of all TEAEs, serious TEAEs, and non-serious TEAEs

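### In Parts A and A1 the non-haematological DLT criterion stops at Grade 4, so a related fatal event in Cycle 1 with no recorded Grade 3 or 4 phase is not a listed DLT, although it would be one in Parts B and C

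*Protocol*

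**What the plan says.** Section 4.1.2.4 defines a Part A DLT as an at least possibly related AE in Cycle 1 that meets any one of four criteria.

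- **Criterion 1** is "Grade 3 or 4 nonhematological toxicity according to the National Cancer Institute (NCI) Common Terminology Criteria for AEs", with exceptions for alopecia and for quickly reversing nausea, vomiting or diarrhoea.
- **Criterion 2** begins "Grade 3 or 4 biochemical abnormality that persists despite maximal supportive treatment". It has a second limb, for symptomatic and non-transient abnormalities, that states no grade.
- **Criterion 3**, for haematological toxicity, is open-ended from Grade 3 upwards, subject to duration or named complications.
- **Criterion 4** covers prolonged or multiple lower-grade toxicities (Grades 1 and 2).

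A closing clause allows investigators to declare a DLT when a participant cannot safely continue treatment. Section 4.1.3 refers to this list for Part A1.

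In sections 4.1.4.2.1 (Part B) and 4.1.5.2.1 (Part C) the corresponding criterion takes any Grade 3 or higher "non-hematological event with the following exceptions". Those exceptions concern certain Grade 3 events only.

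The DLT count is used as follows:

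- Table 3-1 gives the primary endpoints as "Incidence of TEAEs Severity of TEAEs Incidence of DLTs".
- Section 4.1.2.4 places the MTD at the level below one with DLT incidence of 33% or more.
- Section 4.1.2 states: "Escalation can be performed when 3/3, 4/4, 5/5, 5/6, or 6/6 participants are evaluated without a DLT".
- Section 4.1.3 states: "If 3 or more participants experience DLT(s) in a given cohort, no further participants will be enrolled in the cohort".

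**The concern.** A toxicity definition should capture the worst related outcome without anyone having to use discretion. Here the monotherapy definition has an upper limit at Grade 4 for non-haematological events and for the graded limb of the biochemical criterion, and death appears nowhere in the list. The combination parts have no such limit. The same related death would therefore be a listed DLT in Parts B and C but not in the first-in-human parts.

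Several things depend on the label: a primary endpoint, the 33% MTD rule (which caps the RP2D-M under section 4.1.2.5), the requirement that Part A Cohort 5 have a DLT rate below 33% before Part A1 opens, and the Part A1 cohort stop.

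The label also affects evaluability. Section 10.6 treats a participant who leaves before all Cycle 1 UCB6114 doses as nonevaluable and replaceable unless a DLT occurred. The DLT evaluable set in section 10.1 admits early stoppers only when a DLT was the reason. On a literal reading, a death after the first dose could drop out of the denominator as well as the numerator.

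**Working it through.** The protocol states no figure on this point, so there is nothing to reproduce. The check compares the definitions and then does simple arithmetic on the decision rules.

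**1. Which criterion could capture the event?** Take a related, non-haematological fatal event in Cycle 1 with no recorded Grade 3 or 4 phase.

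| Provision | Captures it? |
|---|---|
| 4.1.2.4 criterion 1 | No: Grades 3 and 4 only |
| 4.1.2.4 criterion 2, graded limb | No: Grades 3 and 4 only |
| 4.1.2.4 criterion 2, ungraded limb | Only if it is a symptomatic, non-transient biochemical abnormality |
| 4.1.2.4 criterion 3 | No: haematological |
| 4.1.2.4 criterion 4 | No: Grades 1 and 2 |
| 4.1.2.4 investigator clause | Permits a declaration, does not require one |
| 4.1.4.2.1 and 4.1.5.2.1 (Parts B and C) | Yes: Grade 3 and above |

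**2. Does the protocol treat Grade 4 as including death?** Section 6.6.2.2 refers to "Study participants who experience Grade 4 (life-threatening) nonhematologic toxicity", which describes Grade 4 as life-threatening rather than fatal. The overview table in section 10.3.1 includes "CTCAE Grade 3 or 4 TEAEs, DLTs, AEs leading to death, and TEAEs leading to death", naming deaths apart from Grade 3 or 4 events. The second text is weak evidence, because categories in that table overlap.

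**3. Effect of one uncounted participant on the literal count.**

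Incidence = participants with a DLT / participants in the cohort.

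- Cohort of 6 (Part A): 1/6 = 16.7 percentage points.
- Cohort of 8 (Part A1): 1/8 = 12.5 percentage points.

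*Part A, one other DLT among 6:*

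- Death counted: 2/6 = 33.3%. This meets the 33% rule. 4/6 are without a DLT, which is not on the escalation list in section 4.1.2.
- Death not counted: 1/6 = 16.7%. 5/6 are without a DLT, which is on the list.
- Death removed as nonevaluable: 1/5 = 20.0% until the participant is replaced.

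*Part A1, two other DLTs among 8:*

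- Death counted: 3/8 = 37.5%, which reaches the stop at 3.
- Death not counted: 2/8 = 25.0%, which does not.

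No probability is attached to these cases, because the protocol gives no frequency for such deaths.

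**The case against.** The strongest reply is that these counts would not drive decisions in practice.

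- Section 6.7 suspends the study or part after a single death judged at least possibly related by investigator and sponsor. Enrolment restarts only with an agreed risk mitigation strategy, ethics notification and, where applicable, approval of a substantial amendment.
- The SMC adjudicates individual DLTs (section 4.1.1) and takes all safety data into account (section 4.1.2.2). The escalation list in section 4.1.2 is permissive.
- In Part A1 an ad-hoc SMC meeting follows the first DLT.
- Fatal TEAEs and on-study deaths are reported under section 10.3.1 in any case.
- The event is narrow, since many fatal toxicities pass through a recorded Grade 3 or 4 phase and many haematological deaths fall under criterion 3.
- Grade notation is loose throughout the protocol, which suggests shorthand rather than an intended exclusion of death.

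Most of this stands. It shows that a real miscount is unlikely and that immediate participant safety does not depend on the wording. It also means the 2/6 and 3/8 cases illustrate the written rule and do not forecast what would happen.

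It does not remove the gap. The section 6.7 hold does not classify the death as a DLT, the investigator clause is optional, and the SMC would be adjudicating against a definition that omits the event. If the wording is shorthand, that is a reason to correct it.

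**Conclusion.** The concern holds as a minor gap in a decision rule. Followed exactly as written, section 4.1.2.4 leaves a related non-haematological death in Cycle 1, with no recorded Grade 3 or 4 phase, outside the listed DLTs for Parts A and A1, while Parts B and C include it. For biochemical events the gap is smaller because of the ungraded limb of criterion 2.

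The effect on the literal count is one participant: 16.7 points of DLT incidence in a cohort of 6, or 12.5 points in a cohort of 8. That is enough to cross the 33% rule or the Part A1 stop in the cases shown.

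The conclusion rests on two assumptions: that a fatal event is graded above 4, consistent with the protocol's description of Grade 4 as life-threatening, and that no earlier Grade 3 or 4 phase is recorded. Given the hold and the SMC's role, the practical risk is low.

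**What to change.** In section 4.1.2.4, change the grade range in criteria 1 and 2 to *Grade 3 or higher*, or add a line making any death at least possibly related to study medication a DLT. Either change brings Parts A and A1 into line with sections 4.1.4.2.1 and 4.1.5.2.1, and Part A1 picks it up through the existing cross-reference.

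Sections 10.1 and 10.6 need no edit. Once the event is a DLT, those sections keep the participant evaluable, and section 6.6.1.2 already counts DLTs in replaced participants.

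The cost is a few words. The design, the analysis sets, the sample size and the decision thresholds stay as they are.
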